6.8.10. Vital Signs

Descriptive statistics will be provided for vital sign data (systolic and diastolic blood pressure, heart rate, respiratory rate, body temperature, and oxygen saturation) presented as both actual values and changes from baseline over time. A listing of all vital signs will be provided by patient.

6.8.11. Electrocardiograms

Descriptive statistics will be provided for 12-lead ECG interval data (Heart rate, PR, QRS, QT, and RR) and changes from baseline for each scheduled visit. The average of the triplicates at each visit will be used in the summary. All 12-lead ECG findings will be listed by patient.

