#### 8.9 Electrocardiograms

A 12-lead ECG will be obtained in triplicate at Screening, Days 3, 7, 14 and 42, EOST, and the E/T Visit (if applicable). Patients should be supine for at least 5 minutes prior to the collection of 12-lead ECGs.

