#### 9.2.2 Analysis of Safety

All safety analyses will be performed on the Safety Population. Safety data will be subject to clinical review and summarized by appropriate descriptive statistics. A DSMB will be assigned to monitor safety on an ongoing basis throughout the study.

Analyses will be based on adverse events, vital signs, clinical laboratory assessments, and ECGs. Safety analyses will be descriptive and will be presented in tabular format with the appropriate summary statistics.

A TEAE is defined as an adverse event that started on or after the administration of study drug. The number and percentage of patients with TEAEs will be tabulated by system organ class, preferred term, and by severity and relationship to treatment. Serious adverse events and adverse events leading to discontinuation from study drug will be summarized. Listings will also be provided for SAEs and adverse events leading to discontinuation of study drug.

Descriptive statistics will be provided for clinical laboratory, vital sign, and ECG interval data for both actual values and changes from Baseline over time.

Abnormal physical examination findings will be listed.

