2.3. Study Design

This is a Phase 2, multicenter, open-label, non-comparative study to evaluate the safety and efficacy of fosmanogepix for the treatment of Invasive Mold Infections (IMIs) caused by Aspergillus spp. or rare molds (eg, Scedosporium spp., Fusarium spp., and Mucorales fungi). Patients 18 years of age or older will undergo Screening procedures for up to 5 days, following which eligible patients will participate in the study drug Treatment Period for up to 6 weeks, with a Follow-Up Visit 4 weeks after EOST, and a Follow-Up Phone Call 12 weeks after Day 1 (Day 84). The total duration of a patient's participation in the study will be approximately 12 weeks, inclusive of the follow-up telephone call required on Day 84. Patients who require treatment for longer than 6 weeks can be switched to other licensed antifungal therapy (OLAT) at the discretion of the Investigator and in consultation with the Medical Monitor if the situation allows.

This study will be conducted at up to 40 global sites. The study will enroll male and female patients aged 18 years and above with a confirmed diagnosis of invasive aspergillosis or invasive rare mold infection. Patients will have limited or no treatment options due to documented/anticipated resistance, contraindication, intolerance, or lack of clinical response to standard of care (SOC) antifungal therapy. The study will enroll two cohorts, Cohort A and B. Up to 40 patients will be enrolled in Cohort A, and these patients will have an IMI which was diagnosed according to the EORTC/MSGERC criteria.

Further details of the study design can be found in the protocol.

[figure not shown]

Figure 1. Study Design

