3.5. Baseline Variables

Baseline data will be collected according to the schedule of procedures in the protocol.

For all efficacy and safety endpoints, baseline is defined as the last measurement or assessment prior to first dose of study drug.

For microbiological data, baseline pathogen(s) are *Aspergillus* spp. or rare molds (eg, *Scedosporium* spp., *Fusarium* spp., *Lomentospora* spp., and Mucorales fungi, etc.) isolated from the last positive fungal culture sample collected prior to the first dose of study drug.

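### SAP 6.8.11 summarises QT without a heart-rate correction, so a heart-rate shift from baseline can mask or mimic a change in repolarisation

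*SAP*

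**What the plan says.** SAP 6.8.11 provides descriptive statistics for "12-lead ECG interval data (Heart rate, PR, QRS, QT, and RR) and changes from baseline for each scheduled visit". On the repeat readings it states: "The average of the triplicates at each visit will be used in the summary". It adds: "All 12-lead ECG findings will be listed by patient". The list of parameters is closed and carries no sign of redaction.

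Protocol 9.2.2 is less specific. It promises summaries of "ECG interval data for both actual values and changes from Baseline over time" and leaves the choice of intervals to the SAP.

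The supplied text of both documents, including the abbreviation lists, contains no QTc, no Fridericia or Bazett formula and no category for QT outliers. SAP 2.1 declares no modification to the protocol's analysis.

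Three further statements matter:

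- **Timing.** Protocol 8.9: "A 12-lead ECG will be obtained in triplicate at Screening, Days 3, 7, 14 and 42, EOST, and the E/T Visit". Day 1 is not on the schedule, and neither Protocol 6.3.1 nor Appendix A adds an ECG on that day.
- **Baseline.** SAP 3.5: "baseline is defined as the last measurement or assessment prior to first dose of study drug".
- **Design.** SAP 2.3 describes a "Phase 2, multicenter, open-label, non-comparative study".

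**The concern.** The raw QT interval shortens as heart rate rises and lengthens as it falls. A change from baseline in raw QT therefore combines any change in repolarisation with any change in rate.

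Two features expose this study. With no Day 1 ECG scheduled, the baseline tracing is normally the Screening one, when patients have an active invasive mold infection. Later tracings fall on Days 3, 7, 14 and 42 and at end of treatment, by which time patients may have improved or worsened. SAP 3.2.1.8 scores fever and dyspnea over the study, and both may move with heart rate. There is also no concurrent control arm in which a common drift in heart rate would show, so change from baseline is the only contrast.

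Safety is part of the primary objective in both documents. At stake is whether the one planned QT summary can be read as a statement about repolarisation.

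**Working it through.** The documents give no QT or heart-rate figure, so there is nothing of the plan's own to reproduce. The check asks how large a heart-rate shift would have to be to matter.

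**Inputs.** From the documents: the parameter list, the averaging of triplicates, the ECG schedule, the baseline definition and the single-arm design, all cited above. Assumed: QTcF of 420 ms (range 400 to 440 ms) and heart rates between 80 and 110 bpm.

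**Relation.** Fridericia: QTcF = QT / RR^(1/3), with RR = 60/HR in seconds. Hence QT = QTcF × (60/HR)^(1/3).

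**Mimicking: corrected QT unchanged, heart rate falls to 80 bpm.** At QTcF 420 ms and 80 bpm, QT = 420 × (60/80)^(1/3) = 381.6 ms.

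| Heart rate at baseline | QT at baseline, QTcF 420 ms | Change in raw QT at 80 bpm | Change for QTcF 400 to 440 ms |
|---|---|---|---|
| 90 bpm | 366.9 ms | +14.7 ms | +14.0 to +15.4 ms |
| 100 bpm | 354.2 ms | +27.4 ms | +26.1 to +28.7 ms |
| 110 bpm | 343.2 ms | +38.4 ms | +36.6 to +40.3 ms |

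Every millisecond in the third column comes from rate alone.

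**Masking: corrected QT rises by d ms, heart rate also rises.** From 80 bpm and 420 ms, raw QT is unchanged when (420 + d) × (60/h)^(1/3) = 420 × (60/80)^(1/3), so h = 80 × ((420 + d)/420)^3.

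- d = 10 ms: h = 80 × (430/420)^3 = 85.9 bpm
- d = 20 ms: h = 80 × (440/420)^3 = 92.0 bpm
- d = 30 ms: h = 80 × (450/420)^3 = 98.4 bpm

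If heart rate goes further, the sign reverses. A true 20 ms rise with heart rate moving from 80 to 100 bpm gives 371.1 − 381.6 = −10.5 ms.

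**After correction.** When QTcF is derived per tracing, the change in the table above is 0 ms in every row. That holds by construction, because the same relation generated the numbers. To the extent that real tracings depart from it, some rate dependence would remain.

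**What averaging does.** Taking the mean of three readings reduces measurement noise. It does not remove dependence on rate, because the three tracings share the patient's heart rate at that visit.

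**The case against.** The case on the other side has real content.

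- **Heart rate and RR are summarised at the same visits, and all findings are listed.** A fall in mean rate beside a rise in mean QT would be visible, and no data are lost. This stands as far as it goes. But separate visit means do not give each patient's corrected change, its spread or its extremes. Working them out from listings would be an unplanned, post hoc step.
- **The QT table is not the only ECG safety route.** Under Protocol 8.1, clinically significant ECG findings are reported as adverse events and so reach the tables of SAP 6.8.8. The DSMB also reviews cumulative data. This stands, and it limits what depends on the table.
- **No repolarisation signal is described.** Protocol 1 reports that in three healthy-volunteer studies no ECG result met the criteria for an adverse event, and Protocol 1.2.1 names no cardiac risk. This lowers the stakes but does not make raw QT the better measure.
- **The shifts are assumed.** Individual changes in opposite directions partly cancel in a visit mean, and Protocol 4.2 excludes ventilated patients and those with very low performance status. This also stands: the distortion of a mean depends on the net shift, which the documents do not quantify.

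A reader might infer that heart rate will distort the QT summary, or that the trial's ECG safety conclusion is unreliable in both directions. The documents support neither reading, given the missing heart-rate data and the other ECG safety routes above. Nor is Protocol 9.2.2 in error: its wording, "Descriptive statistics will be provided for clinical laboratory, vital sign, and ECG interval data", does not exclude a corrected QT.

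**Conclusion.** The point holds as a gap in a prespecified descriptive analysis. Following SAP 6.8.11 as written yields a rate-dependent QT change from baseline as the only QT measure, in a single-arm study whose baseline tracing is normally taken during active infection. Heart-rate shifts of roughly 6 to 20 bpm are enough to hide or create a change of about 10 to 30 ms. That size rests on the Fridericia relation and on assumed values of corrected QT and heart rate.

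The word is can, not will: without a net heart-rate shift, the mean change in raw QT is little affected. A corrected QT would not isolate a drug effect either, since underlying disease and other treatments remain uncontrolled in a single arm. It would remove one avoidable source of ambiguity. The mortality test, its alpha and the sample size are not touched.

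**What to change.** In SAP 6.8.11, add QTcF = QT / RR^(1/3), with RR in seconds. Derive it for each tracing, average it over the triplicate, and summarise both the values and the changes from baseline by scheduled visit. Keep the planned summaries of raw QT, heart rate and RR, which help the reader judge how much of any QT change is rate. State that baseline is the last triplicate before the first dose, normally the Screening one.

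Counts of patients above QTcF thresholds, or with increases above a threshold, may be added. Neither document gives cut-offs, so the sponsor would have to choose and prespecify them.

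The cost is one derived variable from data already collected and one table, with no new procedure. The SAP is to be finalised before database lock. If lock has passed, the addition can be documented in the study report, as SAP section 2 provides for deviations.

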6.8.12. Physical Examination

Physical examination including neurological findings will be listed by patient.

7. INTERIM ANALYSIS

No interim analysis is planned for this study.

7.1. Data Review Committee

A DRC comprised of infectious disease experts will adjudicate the diagnosis of IMI at enrollment. This committee will also provide systematic assessment for clinical, mycological, radiological, and global responses at EOST and at the E/T Visit (if applicable).

Global responses will be classified as complete or partial response (categorized as treatment success), stable response, progression of disease, or death (categorized as treatment failure) according to prespecified criteria. Guidelines for the DRC are described in the DRC Charter.

7.2. Data And Safety Monitoring Board

A DSMB comprised of members with pertinent expertise will be responsible for the periodic review of cumulative data from the study as set forth in the DSMB Charter, or more frequently at the request of the DSMB. The DSMB will advise the Sponsor on the continuing safety of patients and those yet to be recruited to the study, as well as the continuing validity and scientific merit of the study. The DSMB may recommend to the Sponsor that dosing in the study be suspended if, in the opinion of the DSMB, further dosing in the study would pose an inappropriate safety risk. Guidelines for what constitutes inappropriate safety risks are described in the DSMB Charter.

8. REFERENCES

Not Applicable.

APPENDICES

Appendix 1. Summary of Efficacy Analyses

Endpoint	Analysis Type	Population	Data Inclusion and Rules for Handling Intercurrent Events and Missing Data	Analysis Model
Primary endpoint: Mortality rate at Day 42.	Primary	mITT	All observed data.	Cohort A: One-sided exact binomial test at the alpha = 0.1 level of significance:
Secondary Endpoint: Global response at EOST	Secondary	mITT	All observed data	Cohort A: Two-sided 80% exact binomial CI
Clinical responses	Other	mITT	All observed data	Cohort A: Two-sided 80% exact binomial CI
Radiological response	Other	mITT	All observed data	Cohort A: Two-sided 80% exact binomial CI
Mycological response	Other	mITT	All observed data	Cohort A: Two-sided 80% exact binomial CI
CCI				

Appendix 2. Data Derivation Details

Appendix 2.1. Definition and Use of Visit Windows in Reporting

The following table defines the visit windows and labels to be used for reporting:

Visit Number	Visit Label	Definition [Day window]
1	Screening	Day -5 to -1
2	Baseline	Day 1
3	Day 2	= Day 2
4	Day 3	= Day 3
5	Day 7	= Day 7, with a window of ± 1 days, (ie, days 6 to 8)
6	Day 14	= Day 14, with a window of ± 1 days, (ie, days 13 to 16)
7	Day 21	= Day 21, with a window of ± 2 days, (ie, days 19 to 23)
8	Day 28	= Day 28, with window from 26 to 30
9	Day 35	= Day 35, with window from 33 to 37
10	Day 42	= Day 42, with window from 40 to 44
11	EOST ²	End of study treatment (Date of last treatment) +2 days
12	FU	(Date of FU) ±3 days
13	FU Phone call	Day 84 ±3 days

Appendix 3. List of Abbreviations

Abbreviation	Definition	
AE	Adverse event	
AspUTest	Aspergillosis urine test	
ATC	Anatomical therapeutic chemical	
BAL	Bronchoalveolar lavage	
BID	Twice daily	
BMI	Body mass index	
CBC	Complete blood count	
CI	Confidence Interval	
CKD-EPI	Chronic Kidney Disease Epidemiology Collaboration	
CSR	Clinical study report	
CT	Computed tomography	
DRC	Data Review Committee	
DSMB	Data and Safety Monitoring Board	
E/T	Early Termination	
ECG	Electrocardiogram	
ECOG	Eastern Cooperative Oncology Group	
eCRF	Electronic Case Report Form	
eGFR	Estimated Glomerular Filtration Rate	
EORTC	European Organization for Research and Treatment of Cancer	
EOST		
IA	End of Study Treatment	
	Invasive Aspergillosis	
IMI	Invasive mold infection	
INR	International normalized ratio	
ITT	Intent-to-Treat	
IV	Intravenous(ly)	
LLN	Lower limit of normal	
LTO	Limited Treatment Option	
MedDRA	Medical Dictionary for Regulatory Activities	
mITT	Modified Intent-to-Treat	
MSG	Mycosis Study Group	
OLAT	Other licensed antifungal therapy	
PCR	Polymerase chain reaction	
PK	Pharmacokinetic(s)	
PO	Oral(ly)	
PT	Prothrombin time	
QD	Once daily	
qPCR	Quantitative polymerase chain reaction	
SAE	Serious adverse event	
SAP	Statistical analysis plan	
SOC	Standard of care	
spp.	Species	
TEAE	Treatment-emergent adverse event	
TRAE	Treatment-related adverse event	
ULN	Upper limit of normal	
WHO	World Health Organization
